For the primary outcome, assuming a Hazard ratio of 2.0 for time to removal of doxycycline vs. conventional treatment and a 1:1 ratio of IPC + doxycycline: conventional IPC patients, then to have 90% power to detect a difference with a two-sided alpha set at 0.05 will require 48 events in each arm (total events=96). The lower border of the 95% CI for catheter removal from our prior study of IPCs was 49%. So if only 49% of patients have their catheter removed for decreased drainage then this will require 196 patients to be enrolled. If 10% of patients drop out then a total of 218 patients will need to be enrolled to generate the 196 patients that will generate 96 events (i.e. catheter removals). We expect dropout rates to be low based on our prior observational study and because the only difference in the intervention arm is a single visit at day 5. Everything else is standard of care. We will be conservative and enroll 250 patients.

Secondary outcomes for pleural fluid recurrence and quality adjusted survival are really exploratory, since the number of events and the magnitude of the effect are likely to be small. For pleural fluid recurrence following catheter removal, we only expect 14% of patients to develop recurrence requiring drainage. Since we have powered the study to have 96 catheter removals, we expect only 14 patients to have fluid recurrence requiring additional intervention. For the secondary outcome of quality-adjusted survival (measured as QALYs), we expect baseline utility to be approximately 0.6 based on our prior study.⁸ In prior multivariate analysis the factors impacting change in utility were chemotherapy or radiation after IPC and severity of baseline dyspnea. Patients with more dyspnea experienced greater improvement in quality adjusted survival since the procedure improved their condition more dramatically. We will use the Kaplan-Meier product-limit method to estimate median QALYs following IPC placement. We will use paired t-test to compare baseline and 1-month Borg scores and utilities. A generalized linear model will be used to evaluate whether other variables have any impact on the pairwise differences between baseline and 1 month.

Data Safety Monitoring Board

The data safety monitoring board will monitor complications in both arms. Based on prior studies conducted at MDACC, 26 of 266 patients (9.8%, 95% CI 6.5% - 14.0%) had one or more complications related to IPC at some point after placement.⁸ Complications included wound site infections (4%), empyema (1%), trapped lung (2%), clogged IPC (3%), dislodgement of the IPC (1%), leakage (0.4%), pain and discomfort (0.4%), kinked IPC (0.4%), and decreased drainage due to sub-pulmonic location (0.4%). We will monitor complications in both arms following randomization (i.e. day 5 onward) to ensure the complications in each arm are not higher than 14% (the upper limit of the 95% CI). It is important to recognize that doxycycline and talc pleurodesis are the two most commonly used sclerosing agents in the United States, so there is a large body of data on doxycycline administered via chest tubes indicating that it is safe. Talc, while more effective, has more risk in terms of ARDS.

In terms of efficacy or futility interim analysis, if efficacy is demonstrated earlier, we will still want to enroll the entire cohort, since the secondary outcomes such as time to fluid recurrence, are exploratory but important, since we will base future power calculations off the exploratory data collected in this study, so it will be worthwhile to collect data on the entire cohort.

With regard to futility, while it is possible the study will not achieve the goal HR of 2.0 for time to removal, a competing risk analysis at MDACC of 266 patients demonstrated the 1-year cumulative incidence of death without catheter removal was 35.7% (95% CI : 29.5% - 42.0%); the 1-year cumulative incidence of catheter removal due to decreased drainage was 51.9% (95%CI: 45.4% - 58.3%); and the 1-year cumulative incidence of catheter removal due to complications or other reason was 7.3% (95% CI: 4.2% - 10.5%).⁸ The median time for catheter removal when it was removed due to decreased drainage was 2 months. Typically after chest tube doxycycline installation on inpatients the chest tube is removed within 1 week. We estimate that since we will be giving the doxycycline at day 5 +/- 2 after IPC placement, and the next follow up is at day 14 and then routine follow up at day 28, that 65-87% of patients will have pleurodesis in the intervention arm. The 65-87% success rate is the estimated rate for doxycycline chest tube pleurodesis (not IPC which has not been done but they should be similar). So our chances of demonstrating clinical success are high.

However, even if we fail to achieve statistical significance, measurement of the HR will be useful in determining future avenues of work, provided the sample size is large enough. If we were to demonstrate early futility, it would not be the same as proving that doxycycline does not work, and the observed sample size at that time point would be too low and the confidence intervals too wide to draw useful conclusions other than that it was unlikely that the study would succeed. If we complete the study to n=250, we should have a more precise representation of the HR which will allow us to evaluate whether we should a) change the sclerosing agent to something more potent (e.g. talc); b) redo the study as a multicenter study using our new estimated HR from this study; or c) a combination of the above. In addition, it may be that a subset of patients (e.g. those that have persistent fluid drainage on day of randomization > 150 ml) will have a benefit, but this will require a larger cohort to look at these subsets.

Budget

We will seek Research-related patient care clinical charges funding (RPCCC) for the 2 patient visits that are not currently part of our standard of care. Pleurodesis for MPE is covered by all carriers and is part of the standard of care, the only part that is not part of the standard of care is the additional visit which is unnecessary for the control arm if this was the standard of care. All drugs and other aspects would be standard of care. The CPT code would be 99212.

Figure 1. Study flow chart

Outpatients with MPE eligible for IPC, consents to trial at time of IPC. There must be no evidence of extensive loculation or hydropneumothorax or other contraindication to pleurodesis or narcotics. IPC placed by “long term” team and a f/u with the pleurodesis team for day 5 +/- 2 is arranged by the research coordinator (Clinic visit with MLP and procedure)

Patient comes in on day 5 \pm 2 and is seen and treated by “pleurodesis team”

- Fentanyl patch 12 mcg/hr in AM. Comes in and gets CXR
- If ECOG \leq 2 AND patient is now an outpatient AND if patient is eligible for pleurodesis – defined as not tremendously loculated by ultrasound and no hydropneumothorax or severe pain after drainage of the effusion (defined as >2 points more than the pain experienced on first day of drainage) or small amount of fluid output despite large amount of fluid being present on CXR with estimated residual volume based on CXR and drainage volume being ≥ 500 ml or other contraindication to pleurodesis AND if there are no contraindications to narcotics then randomize.
- If patient is ineligible for randomization due to above items then take fentanyl patch off and managed as per usual standard of care.

[figure not shown]

Figure 2. Pain Control Algorithm for IPC
Indwelling pleural catheter pleurodesis Pain Control Algorithm.

1. Identify patient for IPC with pleurodesis and consent patient. Obtain baseline measures for Borg, SF6D, and pain instrument, as per usual standard. Consent patient for trial if pleurodesis is feasible (i.e. not tremendously loculated effusion and no hydropneumothorax or trapped lung or other contraindication to pleurodesis).
2. If patient consents schedule f/u appointment for day 5 +/- 2 at the time of IPC placement with pleurodesis team. This is a f/u visit with MLP with a procedure slot booked as well for same day (can be booked as IPC)
3. Give them a fentanyl patch 12 mcg/hour to take home. This is to be placed on day 5 +/- 2 ideally in the morning upon waking up prior to f/u appoint since it takes time to have effect
4. Patient comes in for scheduled visit on day 5 +/- 2 for CXR and then to CPC clinic and is assessed by MLP. Baseline SF6D, pain instrument, Borg as per usual standard. Assuming no dramatic change or infection then goes to procedure area. Nurse places IV.
5. Give pain control with Fentanyl 50 mcg at start of IPC procedure
6. Drain pleural fluid as per usual standard of care until pain or cough.
7. Reassess patient and pain control and give one additional dose of fentanyl 25 mcg if pain VAS 5-7 or fentanyl 50 mcg if VAS is 8-10. If pain level on VAS is 0 – 4 no additional fentanyl is needed.
8. Instill pleurodesis agent (e.g. Doxycycline 500 mg dissolved in 50 ml of normal saline + 25 ml of 1% lidocaine (250 mg))
9. Cap for 1 hour, giving additional doses of fentanyl 25 mcg if pain VAS 5-7 or fentanyl 50 mcg if VAS is 8-10. If pain level on VAS is 0 – 4 no additional fentanyl is needed.
10. If pain control is not adequate, defined as a VAS of 7-10, while in the clinic following IPC after fentanyl total dose is 150 mcg or if there is doubt about maintenance of control then patient goes to pain clinic on the 4th floor for walk in appointment prior to discharge. Pulmonary attending or MLP places consult to pain clinic in orders. Pulmonary recovery area nurse is to put in an online consult and calls the pain clinic at [name] to notify them patient is coming gives hand/off sign out. If there are problems regarding availability then nurse can speak to pain clinic supervisor, [name]. If there is no availability in pain clinic for walk in then the back-up is to send them to EC and have the inpatient pain service come to see as a consult. If this occurs, please place typed note in clinic station using IPC template, delineating need for pain control.
11. If pain control is good, defined as a VAS of 0-4, patient and family receive instruction on pain control algorithm and patient goes home on Hydrocodone 5 mg with acetaminophen 325 mg tablets every 4 hours PRN, dispense 28 tablets (7 days) in addition to the fentanyl patch placed previously. Fentanyl patch should be taken off in 3 days. Follow-up care is as per usual IPC protocol.
12. If pain control is inadequate at home, defined as persistent pain (VAS >= 5) despite use of hydrocodone on more than four occasions in a 24 hour period, patient calls in to pulmonary clinic, speaks to clinic nurse. If pain is the issue, she contacts MLP who assesses patient. If pain management does not require pain clinic (i.e. relatively minor),

MLP and pulmonary attending modify regimen, adjust pain meds, and MLP then follows-up by phone at 24 hours after intervention to verify pain is controlled. If pain is still not controlled patient needs to go to pain clinic. Alternatively if pain is too severe at first contact then patient goes straight to pain clinic at MLP/pulmonary attending discretion. MLP notifies attending pulmonary physician and puts in consult for pain clinic at same time. MLP calls pain clinic at [name] to notify them patient is coming and gives hand/off sign out. If there are problems regarding availability then MLP can speak to pain clinic supervisor, [name]. If there is no availability in pain clinic for walk in then the back-up is to send them to EC and have the inpatient pain service come to see as a consult. If this occurs, please place typed note in clinic station using IPC template, delineating need for pain control so that hand-offs are good. Either way, MLP should document in clinic station with typed or dictated note patient phone encounter, including level of pain (1-10 or VAS), duration, what old pain regimen was (e.g. fentanyl patch 12 mcg/hour and hydrocodone-acetaminophen 5-375 one PO QID PRN) and what the change was (e.g. increase hydrocodone-acetaminophen to 10-375 one PO QID PRN), and plan for f/u.

13. If patient is overly sedated, patient takes off patch early and does not take hydrocodone and calls pulmonary clinic and speaks to MLP. MLP modifies and reviews with attending. MLP does phone call follow-up at 24 hours to verify that modification of regimen works (i.e. pain controlled and not overly sedated).

Pain Clinic info:

4th Floor

Phone [name]

[name], supervisor

Figure 3. Drainage Algorithm of Pleural Fluid after IPC Insertion

[figure not shown]

Figure 4. Management algorithm of IPC malfunctions

[figure not shown]
[figure not shown]

Figure 5. Management algorithm of possible IPC related infections

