4.1 Research Plan and Methods

Study Design:

This is a double blind randomized controlled trial of patients with MPE undergoing IPC placement as part of their standard of care. The Clinical Oncology Research System (CORE) will be used to generate randomization. This will be done immediately after the subject has consented for the protocol.

The primary outcome will be time to pleural catheter removal. Secondary outcomes will include recurrence of effusion requiring drainage in patients that have their IPC removed. Other secondary outcomes will be quality adjusted survival (calculated using the SF-6D to determine utilities and then integrating utilities over time to arrive at quality-adjusted survival), change in

dyspnea (using the Borg score), IPC complications, procedure associated pain, and need for hospitalization due to pain from pleurodesis.¹²

Study Procedures:

The study will prospectively enroll patients being treated for MPE as part of their standard medical care. Note that all measurements are currently part of the standard of care. This includes measurements of QOL, which are captured on the SF-6D for all patients who come to pulmonary clinic. A total of 250 patients undergoing IPC treatment for MPE will be enrolled and randomized in a 1:1 ratio to either IPC + doxycycline or IPC alone. Following enrollment, the schedule of events will be as shown in Figure 1 below. We will obtain informed consent on all patients.

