The study will be blinded to the patient and the long term clinical care management team. After initial consent at the time of IPC placement, research coordinators will arrange for a single extra visit to be made at day 5 +/- 2 for all patients. The reason for the 5 +/- 2 days is to allow patients to come during regular clinic hours rather than on weekends. During this additional visit a different physician team, called the pleurodesis team, will give patients either doxycycline or saline control via the IPC. This team is different than the team that will be making all clinical management decisions. The pleurodesis team will only be giving the drugs on day 5 and managing perioperative pain. In this way all management decisions as to catheter removal, complications, and other aspects of pleural effusion care will be made by the standard clinical care team who will be blinded as to the patient's study status. Patients that receive intrapleural pleurodesis agents, whether it is talc or doxycycline or other agents, sometimes have significant pain during the procedure. The standard of care is to control this with short acting narcotics. But we need to keep the management team blinded as to the use of these narcotics since that might bias their decision making.

A standardized pain control algorithm, developed in conjunction with the pain clinic, will be used. This is shown in figure 2 and this will be used by the pleurodesis team in conjunction with the pain management clinic in the perioperative period to control pain. We will assess pain using a VAS as well.

Subsequent visits will follow the current standard of care algorithms. This dictates how often the catheter is drained and when the catheter is removed and how infections and complications are dealt with. These are all in our current care pathways and will be carried out by the usual clinical team. These are shown in figures 3-5 and cover routine drainage (figure 3), malfunctions (figure 4), and infections (figure 5). Research coordinators will capture this data and do phone call follow-up after the catheters are removed in order to determine if fluid recurs. Patients will be followed for at least 1 year after IPC placement.

Data Collection and Confidentiality Procedures:

The data will be kept in a database on a password-protected computer in a secure office. This information will only be accessible to the study investigators and staff.

Statistical Considerations:

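### A Kaplan-Meier median on the QALY scale makes censoring informative and gives no between-arm effect; a 12-month mean QALY difference would serve the exploratory aim better

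*Combined protocol and SAP*

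**What the plan says.** Section 4.1, Study Design, names quality-adjusted survival as a secondary outcome, with SF-6D utilities obtained for each patient and the QALY formed by "integrating utilities over time to arrive at quality-adjusted survival". Statistical Considerations then gives the analysis: "We will use the Kaplan-Meier product-limit method to estimate median QALYs following IPC placement". No QALY-scale censoring rule, time horizon, between-arm effect measure or confidence interval follows. The only test named for utilities is a paired comparison of baseline with 1 month, and the generalized linear model addresses the same 1-month change.

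On follow-up, Study Procedures says "Patients will be followed for at least 1 year after IPC placement", with no upper limit or data cut-off. The sample size paragraph allows for losses: "If 10% of patients drop out then a total of 218 patients will need to be enrolled". Utilities are "captured on the SF-6D for all patients who come to pulmonary clinic". After catheter removal, the coordinators are to "do phone call follow-up after the catheters are removed in order to determine if fluid recurs"; SF-6D is not mentioned there. The readable text shows no SF-6D schedule to month 12, although some figures are not reproduced.

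The plan calls the QALY outcome exploratory. The Data Safety Monitoring Board section says that exploratory data from this trial will feed future power calculations.

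**The concern.** The product-limit estimator assumes that a patient censored at a given value has the same future as those still at risk at that value. Administrative censoring may satisfy this in calendar time. It does not carry over to QALYs, because the censoring point becomes utility multiplied by follow-up time. Patients with low utility are censored at low QALY values, and they are also the patients who would have accrued further QALYs slowly. Removing them from the risk set pushes the curve upward. The condition for this is present here: the plan itself reports that change in utility varied with baseline dyspnea and with later chemotherapy or radiation.

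The second part does not depend on the size of that bias. A randomized trial with quality-adjusted survival as a named secondary outcome should state how the arms will be compared on it. A median per arm supplies neither a mean difference nor a standard deviation, which a later sample size calculation would need. If survival is long relative to follow-up, the median may not be reached at all.

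**Working it through.** **Inputs.** From the documents: "we expect baseline utility to be approximately 0.6 based on our prior study"; follow-up of at least 1 year; 10% dropout; 250 patients allocated 1:1. Assumed, because the documents are silent: exponential survival with median 4 to 18 months, utility SD 0 to 0.15, utility linked or not linked to survival, and follow-up of exactly 1 year or spread evenly over 1 to 3 years.

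The documents bound survival only loosely. In the earlier cohort 35.7% died by 1 year with the catheter in place. Deaths after removal come on top, so 1-year survival was at most 100 − 35.7 = 64.3%. Under exponential survival that caps the median at 12 × ln 2 / −ln 0.643 = 8.318 / 0.4416 ≈ 19 months.

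**The plan's own figures.** No sample size or power is given for QALYs. The primary-outcome numbers reproduce: (1.960 + 1.282)² × (2 + 1)² / (2 − 1)² ≈ 94.6, hence 95, or 96 in two equal arms; 96 / 0.49 ≈ 196; 196 / 0.90 ≈ 218. The point does not rest on them.

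**Why the size depends on survival.** With no dropout, the earliest censoring on the QALY scale is U × 1 year. The median QALY is roughly 0.6 × (median survival in months / 12). With utility SD 0.15:

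- 6 months: 0.30. Censoring below the median needs U < 0.30, which is (0.60 − 0.30) / 0.15 = 2 SD below the mean.
- 9 months: 0.45, which is 1 SD below.
- 12 months: 0.60, which is the mean, so about half of the 1-year survivors can be censored below the median.
- 18 months: 0.90, which is 2 SD above, so nearly all 1-year survivors are censored before the median.

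**Simulated bias of the Kaplan-Meier median QALY** (400,000 patients per scenario, dropout 0 or 10% per year):

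| Median survival | Follow-up exactly 1 year | Follow-up 1 to 3 years |
|---|---|---|
| 4 to 6 months | 0 to 0.5% | 0 to 0.5% |
| 9 months | about 0 to 1.6% | about 0 to 1.6% |
| 12 months | about 3 to 9% with utility SD 0.12 to 0.15; down to 1.2% with less spread | 0 to 1.4% |
| 18 months | median not reached in 9 of 10 scenarios | 0 to 4.5% |

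One unfavourable case at 12 months (SD 0.15, linked utility, 10% dropout, exactly 1 year): true median 0.557, Kaplan-Meier 0.603, and 0.603 / 0.557 − 1 = 8.3%. If follow-up runs from 1 to 2 years, the 12-month figure rises to at most about 2.4%. If all patients have the same utility and the median is reached, the bias is nil or negligible.

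**Between arms.** With mean utility 0.60 against 0.65 and equal survival, the Kaplan-Meier difference in medians was within 0.003 QALY of the truth wherever it could be estimated. The largest gap was 0.0706 − 0.0679 = 0.0027. If the arms share utility, survival and censoring, the bias cancels.

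**The replacement.** With no dropout and utilities fully known, the mean 12-month QALY had 0.0% bias. With 10% dropout per year, an analysis of complete cases alone was biased by −1.3% to −3.0%, because patients who die early are more often complete. Hence the need for weighting.

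Precision: 250 × 0.9 / 2 ≈ 112 per arm and SD about 0.25 give a standard error of 0.25 × √(2/112) = 0.0334. The detectable difference at 80% power is (1.960 + 0.842) × 0.0334 ≈ 0.094 QALY. Power for a difference of 0.03 is Φ(0.03 / 0.0334 − 1.960) ≈ 14%.

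**The case against.** The strongest defence is that the bias hardly matters. Patients with malignant effusion may have short survival, in which case it is well under 2%. The larger figure needs a median survival near 12 months together with a cut-off at exactly 1 year, whereas the plan says at least 1 year. Even then, with SD 0.12 and no dropout, a bias of 0.018 to 0.042 QALY lies below a per-arm standard error of about 0.09 at 112 patients. The outcome is exploratory, a median is a legitimate summary, and it allows comparison with the earlier cohort. All of this stands and limits the point's importance. It does not supply the missing between-arm effect.

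Two stronger readings are tempting. A reader might infer that the planned treatment comparison of QALYs is materially biased. No such bias was found, although only a contrast in mean utility with equal survival was tried. A reader might also infer that the follow-up rule makes an unbiased 12-month QALY available for nothing. The documents do not support that. One year is a plan, 10% loss is budgeted for, and being in follow-up is not the same as having a utility. SF-6D is tied to clinic attendance, contact after removal is described as telephone calls about fluid, and the earlier cohort's median time to removal for decreased drainage was 2 months.

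The gap in SF-6D does not favour the present method, however. Integrating utilities over time needs the same measurements, and needs them beyond month 12 for longer survivors.

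**Conclusion.** The point holds as a minor one. On the QALY scale the product-limit estimator is not consistent in general when utilities differ between patients, and the plan gives no between-arm effect for a named secondary outcome. The bias in the median is under about 2% if median survival is 9 months or less, and about 3 to 9% upward if it is 12 months with all patients censored at exactly 1 year. Little bias in the difference between arms has been shown. These sizes rest on assumed exponential survival, a utility constant within each patient, assumed utility spread and its link to survival, and an assumed follow-up limit. The more practical reasons to change are the missing effect measure and the chance that the median is not reached. The outcome remains exploratory under either method.

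**What to change.** Amend the quality-adjusted survival text in Statistical Considerations to say:

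- The exploratory QALY analysis compares the arms by the difference in mean QALYs accrued from IPC placement through 12 months, with utility 0 after death, and reports a bootstrap 95% CI and the SD per arm.
- Dropout before month 12 is handled by inverse-probability-of-censoring weights.
- Missing SF-6D in patients still followed is handled by a stated method, such as interpolation between assessments or multiple imputation. Weights for dropout do not cover this case.
- The Kaplan-Meier median QALY is retained as a descriptive summary, for comparison with the earlier cohort.

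State alongside this when SF-6D is collected through month 12, including after catheter removal.

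The cost is a few sentences of analysis text, plus scheduled SF-6D assessments if none exist, which the planned QALY already requires. The estimand becomes a 12-month restricted mean, QALYs after month 12 are not used, and validity depends on the dropout model and on SF-6D availability to month 12.

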significant complications including ARDS (8% in the thoracoscopic talc group and 4% in the chest talc group).⁵ This led to questions regarding talc's safety, whether delivered by chest tube or thoracoscopy. In addition, the meta-analyses noted above^{3,4} did not include IPCs, so how IPCs compare to thoracoscopic pleurodesis is not as well studied.

IPCs (IPCs) were pioneered at M.D. Anderson. They have been shown to be effective in relieving dyspnea and improving QOL.^{1,6-8} The main complication is catheter infection, which is fairly uncommon and can usually be treated with outpatient antibiotics. Typically about two thirds of patients with IPCs will eventually have decreased drainage, usually several weeks to months after initial placement. Once drainage is minimal, the IPC is typically removed. This is done according to a standard management algorithm. Once removed, the fluid usually does not recur. Of note, IPCs management strategies have not typically involved the use of any pleurodesis agent, but rather pleurodesis is achieved "spontaneously" after prolonged drainage. In addition IPC's allow patients to be treated completely in the outpatient setting, which is a significant advantage compared to thoracoscopic and chest tube pleurodesis techniques. A recent randomized controlled trial of IPCs vs. chest tubes with talc slurry found no significant difference in terms of dyspnea relief at 42 days between the two groups, but dyspnea relief was better at 6 months in the IPC group.⁹ However, current evidence based guidelines are not definitive as to which approach is best.¹

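### Borg and utility are tested as a within-patient change from an undefined baseline, with no stated arm comparison, so the planned test does not answer the doxycycline question

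*Combined protocol and SAP*

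**What the plan says.** The combined protocol and SAP, section 4.1 (Study Design), lists change in dyspnea on the Borg score and SF-6D-based quality-adjusted survival among the secondary outcomes. Under Statistical Considerations the method given for the scores is: "We will use paired t-test to compare baseline and 1-month Borg scores and utilities". One further model follows: "A generalized linear model will be used to evaluate whether other variables have any impact on the pairwise differences between baseline and 1 month". Neither sentence names treatment arm or the visit that supplies the baseline. Nor do they say whether 1 month runs from catheter placement or from instillation.

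Figure 2 (pain control algorithm) records the same instruments under the same label at two visits. Step 1, at consent: "Obtain baseline measures for Borg, SF6D, and pain instrument, as per usual standard". Step 4, at the day 5 +/- 2 visit, before that day's drainage (step 6) and instillation (step 8): "Baseline SF6D, pain instrument, Borg as per usual standard".

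The plan expects the catheter alone to move these scores. Section 2.1 says of indwelling catheters: "They have been shown to be effective in relieving dyspnea and improving QOL". Section 4.1 says of the earlier catheter-only cohort: "Patients with more dyspnea experienced greater improvement in quality adjusted survival since the procedure improved their condition more dramatically".

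The time of randomization is given in two ways. Section 4.1 (Study Design) says: "This will be done immediately after the subject has consented for the protocol". Figure 1 puts it at the day 5 visit, after an eligibility check: "AND if there are no contraindications to narcotics then randomize".

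**The concern.** A paired t-test asks whether patients changed. The trial asks whether patients given doxycycline changed differently from those given saline. Every patient receives a catheter, and the documents expect the catheter to help, so a paired test can be clearly significant when doxycycline does nothing.

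The undefined baseline makes this worse. Between steps 1 and 4 the patient has the catheter placed and spends 3 to 7 days with it. The two candidate changes therefore measure different things, and the analyst could choose between them after seeing the data. The Data Safety Monitoring Board section says that exploratory data from this study will feed later power calculations, so an ambiguous secondary result would be carried forward.

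**Working it through.** **The plan's own figure.** There is no power calculation for Borg or utility. The only one is for the primary outcome. Freedman's formula with hazard ratio 2.0, 90% power and two-sided 0.05 gives (1.960 + 1.282)² × (3/1)² = 10.51 × 9 = 94.6 events. That is 47.3 per arm, rounded up to 48, or 96 in total. Then 96/0.49 = 195.9, so 196 patients, and 196/0.90 = 217.8, so 218. The plan's figures are reproduced, and nothing below touches them.

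**What each change contains.**

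| Change to 1 month | Shared by both arms | Isolates doxycycline within patient? |
|---|---|---|
| From step 1 (consent) | Placement, first drainage, later drainage | No |
| From step 4 (day 5 +/- 2) | Drainage after day 5 | No |
| Either, compared between randomized arms | Cancels in expectation | Yes, between arms |

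That step 1 comes before placement is inferred from the order of steps 1 and 2 and from Figure 1, which puts consent at the time of the catheter. No sentence says so outright.

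**How often the paired test is significant when doxycycline does nothing.** The documents give no standard deviation, correlation or size of catheter effect, so these are assumptions. Let both arms shift by c SD, with within-patient correlation r and equal SDs. The expected test statistic is c√n / √(2(1 − r)), and rejection is two-sided at 0.05. Worked case: n = 100, c = 0.2, r = 0.3 gives 2/√1.4 = 1.69, and the rejection probability is 39%.

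| Pairs | c = 0 | c = 0.2 (r = 0.3 to 0.6) | c = 0.5 (r = 0.3 to 0.6) |
|---|---|---|---|
| 100 | 5% | 39–61% | 99–100% |
| 196 | 5% | 66–88% | about 100% |

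These are not errors of the t-test, because the shift is real. They are detections of something other than doxycycline.

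**Precision of a between-arm comparison.** In SD² units, a change score has variance proportional to 2(1 − r) and a covariate-adjusted 1-month value to 1 − r². The assumed correlations with the 1-month score are 0.2–0.4 for the placement value and 0.4–0.7 for the day 5 value.

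- Change from placement: 2(1 − 0.4) = 1.2 to 2(1 − 0.2) = 1.6.
- Adjusted for placement: 1 − 0.16 = 0.84 to 1 − 0.04 = 0.96.
- Adjusted for day 5: 1 − 0.49 = 0.51 to 1 − 0.16 = 0.84.

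Adjusting instead of subtracting, at placement, is worth 1.2/0.84 = 1.4 to 1.6/0.96 = 1.7 times the sample. Adjusting for day 5 instead of placement is worth 0.84/0.84 = 1.0 to 0.96/0.51 = 1.9 times. With both values in the model, the residual variance is in principle no larger than with the better one alone. The exact gain needs the correlation between the two early values, which is a further unknown, so it is not computed.

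**The case against.** The strongest reply is that the intent is clear and the ambiguity slight. Statistical Considerations opens by saying that the aim is to see how the intervention affects outcome, and lists dyspnea. The other variables in the generalized linear model could include treatment arm. Baseline most naturally means the placement visit: the expected utility of about 0.6 comes from a cohort undergoing catheter placement, and QALYs are counted from placement. Step 4 sits in a pain algorithm, where the word may mean only a pre-procedure reading. These are secondary outcomes of a study seeking preliminary data. All of that is fair, and it limits the severity. It does not supply the missing sentence: no method for comparing these scores between arms is stated.

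Three stronger readings are tempting, and the documents do not support them.

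- A reader might infer that only the day 5 value can separate doxycycline from the catheter, and that a change from placement is uninterpretable. Both values precede instillation, so a catheter benefit common to the arms cancels between arms from either one. Within patients, day 5 does not isolate the drug either, because drainage continues.
- A reader might set change from placement directly against day 5 adjustment and claim 1.2/0.84 = 1.4 to 1.6/0.51 = 3.1 times the sample. That range mixes two decisions. Its lower end comes wholly from covariate adjustment. The choice of visit alone gives 1.0 to 1.9, which includes no gain, and the higher day 5 correlations are assumed.
- A reader might infer that the two changes differ greatly or even in sign. The cohort statement is comparative and concerns quality-adjusted survival. No Borg change is given.

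**Conclusion.** The point holds. As written, the Borg and utility analysis is a within-patient test from an unspecified baseline, and neither candidate baseline makes it a test of doxycycline. The main defect is the missing arm comparison. The double label is secondary and, once arms are compared, bears on precision and not on bias.

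The size rests on assumptions. With a shared shift of 0.2 SD and no drug effect, the paired test is significant in 39–61% of trials with 100 pairs and 66–88% with 196. The day 5 covariate is worth 1.0 to 1.9 times the sample against the placement covariate. Adjustment in place of change scores is worth about 1.4 to 1.7 times at placement. The change is worth making, but it concerns secondary outcomes only.

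**What to change.** In section 4.1, Statistical Considerations:

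1. Make the analysis of 1-month Borg and utility a between-arm ANCOVA: the 1-month value on treatment arm, with the day 5 value (before that day's drainage and instillation) and the placement value as covariates. State the time origin and window of the 1-month value.
2. Keep the paired change from placement, labelled as a description of the catheter effect.
3. Keep the placement utility as the start of the QALY calculation.
4. Give the step 1 and step 4 measurements in Figure 2 different names.
5. Reconcile the time of randomization between Study Design and Figure 1. If it is at consent, keep patients with no day 5 value in the analysis by using their placement value.

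The cost is wording, since Figure 2 already collects both measurements. There are two small downsides. Day 5 values are taken with the fentanyl patch on, in both arms, so they are not untreated readings. Some day 5 values may also be missing, which matters most if randomization comes before that visit.
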